[figure not shown]

[figure not shown]
**A Research on the Clinical Significance of Sentinel Lymph Node
Imaging Combined With Imaging Examination in Pelvic and
Peritoneal Lymphadenectomy for Endometrial Carcinoma**

2019.02.01

Study objectives The primary objective of this study is to identify the specific number and percentage of pelvic and abdominal lymph nodes that are invaded by metastatic endometrial carcinoma, and to calculate the coincidence rate of lymph node imaging and pathological examination. By setting up the control group and experimental group, we plan to find out whether pelvic and abdominal lymphadenectomy would exert positive effect on patients with endometrial carcinoma.

Trial design This is a prospective interventional trial. After signing of informed consent, the electronic medical data of patients with endometrial carcinoma will be collected in this study. The specific number and percentage of pelvic and abdominal nodes that are invaded by tumor cells will be calculated. By combining the imaging results and pathological test, we plan to obtain the coincidence rate of three tests. Finally, we would randomize patients into the control group and the experimental group as to receive the pelvic and peritoneal lymphadenectomy. When their postoperative data such as the reoccurrence rate and the five year survival rate are compared, the effect of pelvic and peritoneal lymphadenectomy on the prognosis of endometrial carcinoma are drawn.

Sample size The planned sample size was based on data from a previous study, in which the standard deviation was 5. We assumed an one-tailed α error of 0.05 and a sampling error of 1.0. We propose to enroll 70 participants including 35 patients in the control group and the others in the experimental group, and allow for a dropout rate of 10% for an effective sample size of 60.

Inclusion criteria

1. Volunteer to participate in the study with informed consent;
2. Females aged 10-90 who are confirmed with endometrial carcinoma and are willing to receive primary non-reserved fertility function surgery.

Exclusion criteria

1. Pregnancy, lactation, postmenopause, or planned pregnancy within two years;
2. Suspected or identified as other tumors of genital tract;
3. History of hyperparathyroidism, infectious diseases (tuberculosis, AIDS), autoimmune diseases, or digestive system diseases (malabsorption, crohn disease and dysentery);
4. Other diseases or heavy injuries that will interfere with the results;

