5. Simultaneous participation in another clinical study with investigational medicinal product(s) or researcher thinks the subjects are not suitable for this trial.

Withdrawal Subjects must be withdrawn from the study when one of the following criteria occurs:

1. At their own request. At any time during the study and without giving reasons, a subject may decline to participate further. The subject will not suffer any disadvantages as a result;
2. In the investigator's opinion, continuation of the study treatment would be harmful to the subject's health;
3. Obvious non-compliance;

4. Lost to follow-up;
5. Pregnancy;
6. Other medical or surgical treatments of endometrial carcinoma.

Safety assessments

Safety will be assessed by renal and liver function test, electrolyte, routine blood test. Other indicators are detected during the operation and rehabilitation period. The occurrence of any adverse events in participants will be recorded in the case report forms during each patient visit. We will withdraw patients who have severe adverse events, as it is unsafe for them to continue the trial. Meanwhile, we will give them relevant medical care and follow them up until the reaction has terminated.

Statistic analysis

The specific number and percentage of pelvic and abdominal lymph nodes that are invaded by tumor cells are collected. Multiple linear regression analysis was applied to evaluate the risk of lymphatic metastasis related to fourteen independent variables including four qualitative variables (hypertension, diabetes, diagnosis according to the FIGO staging system and the pathological tumor type) and eight quantitative variables (age, BMI, the number of lymph nodes, the interval between biopsy and operation, surgical time, surgical bleeding, postoperative anticoagulant time, preoperative value of Hb, preoperative value of RBC and preoperative value of Hct). All statistical analyses were performed by SPSS 17.0 software package and the level of statistical significance was set at $P < 0.05$. All independent variables were incorporated into the model using the method of "Enter". Data are presented as mean \pm standard deviation. Meanwhile, we collect the lymph node imaging results and the pathological test results so as to investigate the coincidence rate of the three examinations by chi test. As to the analysis of the lymphadenectomy on patients, we would conduct corresponding statistical method to interpret the follow-up data.

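### The withdrawal rules, on their natural reading, can remove patients from the randomised recurrence and five-year survival comparison for reasons linked to prognosis or assigned surgery, and no analysis set guards against it

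*Combined protocol and SAP*

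**What the plan says.** Study objectives in the combined protocol and SAP sets up two groups because "we plan to find out whether pelvic and abdominal lymphadenectomy would exert positive effect on patients with endometrial carcinoma". Trial design draws that effect from recurrence and five-year survival in the randomised groups, 35 patients in each (Sample size).

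The Withdrawal section is mandatory and refers to the study as a whole, not to study treatment: "Subjects must be withdrawn from the study when one of the following criteria occurs". The third of its six criteria is "Obvious non-compliance" and the sixth is "Other medical or surgical treatments of endometrial carcinoma". The second turns on whether "continuation of the study treatment would be harmful".

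Safety assessments adds a further trigger: "We will withdraw patients who have severe adverse events, as it is unsafe for them to continue the trial". The only follow-up described for these patients is to "follow them up until the reaction has terminated".

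For the randomised comparison, Statistic analysis says only that "we would conduct corresponding statistical method to interpret the follow-up data". It gives no analysis set, no censoring rule and no rule for missing status. The 10% dropout allowance appears only under Sample size.

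**The concern.** Severe events may depend on whether lymphadenectomy was done. Non-compliance may depend on the assigned arm. Other cancer treatment may follow high-risk pathology, or the recurrence that is itself an outcome. If such patients leave the study and nobody records what happens to them, the groups compared at five years are no longer the groups that were randomised.

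The scope of the sixth criterion is unclear. It may mean only treatment that replaces the study operation. As worded it could also cover adjuvant treatment and treatment of a recurrence, and the inclusion criteria set no stage limit that would make these rare. The severe-event and non-compliance rules raise the question whichever way the sixth criterion is read.

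Because no handling rule is stated, the choice between censoring withdrawn patients, leaving them out and counting them as failures would be made after the data are seen. The working shows that these choices can give very different answers from the same patients.

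**Working it through.** The plan gives no withdrawal, recurrence or survival rate for this comparison, so it has no figure to reproduce. Its dropout allowance (0.10 × 70 = 7 patients) only sizes enrolment. From the documents come 35 patients per arm and the five-year horizon. **Every rate below is a reviewer assumption, used to show what the rules could do.**

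**Illustration 1: applies only if the sixth criterion covers treatment of recurrence.** Assumed: five-year recurrence 25% in one arm and 10% in the other, median survival after recurrence 1.5 years, 3% other deaths by five years, exponential times.

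- Hazards per year: recurrence λ = −ln(0.75)/5 = 0.0575 and −ln(0.90)/5 = 0.0211; death after recurrence μ = ln 2/1.5 = 0.4621; other death ω = −ln(0.97)/5 = 0.0061.
- Alive without recurrence: a = 0.97 × 0.75 = 0.7275 and 0.97 × 0.90 = 0.8730.
- Alive after recurrence: b = 0.97 × [λ/(μ−λ)] × (e^(−5λ) − e^(−5μ)) = 0.97 × 0.0926 = 0.0898 and 0.97 × 0.0383 = 0.0371.
- True five-year survival a + b = 81.7% and 91.0%, a difference of 9.3 points.
- Recurrence by five years: R = [λ/(λ+ω)] × (1 − a) = 0.2464 and 0.0985.

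Suppose a fraction p of recurrences is withdrawn at recurrence. Counted as failures, survival reads a + (1−p)b. With withdrawn patients excluded, it reads [a + (1−p)b]/(1 − pR). Censored, it is the Kaplan-Meier value from the hazard among those still observed, integrated numerically; at p = 1 that is simply 97.0% in each arm. Patients withdrawn number 35 × (p₁R₁ + p₂R₂). Differences are taken before rounding.

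| Recurrences withdrawn (25% arm / 10% arm) | Censored | Excluded | Counted as failures | Patients withdrawn |
|---|---|---|---|---|
| 100% / 100% | 97.0 vs 97.0: 0 | 96.5 vs 96.8: 0.3 | 72.75 vs 87.3: 14.6 | 12.1 |
| 50% / 50% | 88.7 vs 93.9: 5.2 | 88.1 vs 93.8: 5.7 | 77.2 vs 89.2: 11.9 | 6.0 |
| 25% / 75% | 85.1 vs 95.4: 10.4 | 84.7 vs 95.3: 10.6 | 79.5 vs 88.2: 8.7 | 4.7 |
| 100% / 50% | 97.0 vs 93.9: −3.1 | 96.5 vs 93.8: −2.8 | 72.75 vs 89.2: 16.4 | 10.3 |

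The first row is the mandatory rule applied in full. The last two rows only show that direction is not fixed; the documents give no basis for unequal rates.

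A recurrence that triggers withdrawal has already been seen. The recurrence comparison therefore changes only if withdrawn patients are excluded: with half withdrawn, recurrence among those kept is (1−p)R/(1−pR), so 24.6% vs 9.9% becomes 14.1% vs 5.2%. Otherwise the loss is mainly later survival.

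**Illustration 2: applies under either reading of the sixth criterion.** Patients with severe events are excluded. Assumed: severe events in 5% vs 15%, or 10% vs 30%, with 20% recurrence. The same formulas give five-year survival of 84.9% at that baseline, 74.6% at twice the recurrence hazard and 66.0% at three times.

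- *Severe events raise the recurrence hazard.* The true harm runs from (84.9 − 74.6) × 0.10 = 1.0 to (84.9 − 66.0) × 0.20 = 3.8 points. After exclusion both arms read 84.9%, a difference of 0.
- *Severe events only mark worse prognosis, with overall recurrence 20% in both arms.* Recurrence r in patients without events solves (1−q)(1−r) + q(1−r)^HR = 0.80, where q is the severe-event rate. For 5% vs 15% at hazard ratio 2, r is 19.2% vs 17.8%; for 10% vs 30% at hazard ratio 3, 17.4% vs 13.5%. Survival moves about (91.0 − 81.7)/(25 − 10) = 0.62 points per point of recurrence. A true difference of about 0 then reads 1.4 × 0.62 = 0.9 to 3.9 × 0.62 = 2.4 points in favour of the arm with more severe events.
- *Severe events unrelated to prognosis.* No bias.

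Patients with severe events: 35 × (0.05 + 0.15) = 7, or 35 × (0.10 + 0.30) = 14. Non-compliance and adjuvant treatment are not quantified.

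**Precision.** The 95% half-width for the survival difference at 35 per arm is 1.96 × √(0.817 × 0.183/35 + 0.910 × 0.090/35) = 0.159, about ±16 points.

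**The case against.** The strongest reply is that loss of outcomes is inferred. Nowhere do the documents say that recurrence or vital-status checks stop at withdrawal. The phrase "follow them up until the reaction has terminated" sits under Safety assessments and may describe only how long an adverse reaction is monitored. This stands, and it lowers confidence that outcomes would be lost. It does not remove the point: leaving the study is naturally read as ending follow-up, and no sentence provides for outcomes afterwards.

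Second, the sixth criterion may be narrow. The second criterion's reference to study treatment suggests that it could mean only treatment replacing the study operation. On that reading Illustration 1 falls away, and only the smaller severe-event shifts and the unquantified non-compliance rule remain. This also stands.

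Third, the stated primary objective, nodal involvement and agreement between imaging and pathology, is measured around surgery and is largely unaffected. The survival interval is also wider than any bias shown. Both are true. They limit the consequence, but the randomised comparison is still a stated aim and the reason for having two groups.

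A reader might infer that the protocol orders outcome follow-up to stop, or that the rules must shrink, or must favour, the effect of lymphadenectomy. The documents support neither. The first is not stated, and the table shows the difference shrinking, growing or reversing according to who is withdrawn and how they are counted.

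**Conclusion.** The point holds for the randomised comparison only. Confidence is high that the documents state neither an analysis set nor any provision for outcomes after withdrawal, and moderate that outcomes would in fact be lost.

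Neither the size nor the direction of the bias can be read from the documents. It could be large under the broad reading of the sixth criterion and is at most a few points for severe events under the rates assumed here; it is nil for severe events if they are unrelated to prognosis. This is an avoidable weakness that should be fixed, not one that invalidates the trial. Removing it would not by itself make a comparison of 35 patients per arm informative on survival.

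**What to change.** - State that the withdrawal criteria, including the severe-event rule, end study procedures and not the collection of outcomes.
- Reconcile the scope of the sixth criterion with the five-year comparison, and record any later cancer treatment as data.
- Follow every randomised patient for recurrence and vital status to five years, unless she withdraws consent for follow-up.
- Analyse all randomised patients as allocated, with a stated rule for missing status.

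No clinical management rule changes; only data collection and the analysis set do.

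The cost is a short amendment plus status checks on withdrawn patients, at most the 70 enrolled. Under the illustrations that is about 5 to 12 patients for the sixth criterion and 7 or 14 for severe events, before overlap and without non-compliance.

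### The primary percentage counts lymph nodes and agreement is assessed only by a chi test, with no stated unit of analysis and no allowance for several nodes per patient or for paired readings

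*Combined protocol and SAP*

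**What the plan says.** The Study objectives section gives the primary objective two parts. The first reads "identify the specific number and percentage of pelvic and abdominal lymph nodes that are invaded by metastatic endometrial carcinoma". Taken literally, this has lymph nodes in both numerator and denominator, and the Trial design section repeats it. The second part reads "to calculate the coincidence rate of lymph node imaging and pathological examination".

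The Statistic analysis section says of the first part only that "The specific number and percentage of pelvic and abdominal lymph nodes that are invaded by tumor cells are collected". For the second part it proposes to "investigate the coincidence rate of the three examinations by chi test". It does not list the three examinations, name the variant of the test, or say whether a row of data is a node or a patient. The significance level is P < 0.05, with sidedness not stated. The only rule for showing spread is mean ± SD; no confidence interval for a percentage is mentioned.

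The same section lists the node count as a quantitative covariate, so patients are expected to contribute differing numbers of nodes. Neither document section mentions clustering, a patient-level metastasis endpoint, robust variance, GEE, mixed models or a method for paired data. The Sample size section counts patients (70 enrolled, 60 effective) and has no design effect.

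**The concern.** Two dependencies are left unaddressed.

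- **Several nodes per patient.** Nodes from one patient share a tumour, a stage and a surgeon, so their results are likely to be correlated. If nodes are pooled, the information is closer to that of 60 or 70 patients than to that of several hundred independent nodes. Patients with more nodes removed also weigh more: one with 20 nodes counts twice as much as one with 10.
- **Paired readings.** Imaging and pathology are read on the same nodes or the same patients. An ordinary chi-square either tests whether two readings are associated, which is not how well they agree, or compares two positivity rates as if they came from separate samples. This problem is present whichever unit is used.

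Both bear on the primary objective. With the unit left open, the analyst could also choose it after seeing the data, and the pooled percentage and the mean of per-patient percentages can differ.

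**Working it through.** **1. The plan's own figure.** The Sample size section gives an SD of 5 ("in which the standard deviation was 5") and says "We assumed an one-tailed α error of 0.05 and a sampling error of 1.0". The one-sided precision formula for a mean gives n = (z × SD / error)² = (1.645 × 5 / 1.0)² = 67.6, so 68, or 70 with the t quantile. The planned 70 is therefore reproduced as a number of patients, with nothing added for nodes within patients. The variable that has the SD of 5 is not named. (70 × 0.9 = 63, not 60; that is a separate matter and changes nothing here.)

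**2. Inputs for the clustering check.** The number of patients, 60, is from the Sample size section. Nodes per patient (m), ICC, node positivity and imaging accuracy are assumptions, because the documents give none of them. I take m = 10 and 20 and ICC = 0.1 to 0.3.

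**3. Formulas.**

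- Pooled node percentage: design effect DE = 1 + (m − 1) × ICC. A naive interval is too narrow by √DE, and its true coverage is 2Φ(1.96/√DE) − 1.
- Node-level chi-square for association between imaging and pathology: DE = 1 + (m − 1) × ICC(imaging) × ICC(pathology). The true error rate at nominal 5% is 2 × (1 − Φ(1.96/√DE)).

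**4. Results**, with the same ICC for both readings in the last two columns:

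| m | ICC | DE, percentage | √DE | Coverage of naive 95% interval | DE, association | Error rate, association |
|---|---|---|---|---|---|---|
| 10 | 0.1 | 1.9 | 1.38 | 84.5% | 1.09 | 6.0% |
| 10 | 0.2 | 2.8 | 1.67 | 75.9% | 1.36 | 9.3% |
| 10 | 0.3 | 3.7 | 1.92 | 69.2% | 1.81 | 14.5% |
| 20 | 0.1 | 2.9 | 1.70 | 75.0% | 1.19 | 7.2% |
| 20 | 0.2 | 4.8 | 2.19 | 62.9% | 1.76 | 14.0% |
| 20 | 0.3 | 6.7 | 2.59 | 55.1% | 2.71 | 23.4% |

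Example: 60 patients with 20 nodes each give 1,200 nodes. With 10% of nodes positive, the naive half-width is 1.96 × √(0.1 × 0.9 / 1200) = 1.7 percentage points. At ICC 0.2 it should be 1.7 × 2.19 = 3.7 points, and the 1,200 nodes carry the information of 1200 / 4.8 = 250.

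Over a wider range (m = 10 to 30, ICC 0.05 to 0.5) the percentage DE runs from 1.45 to 15.5 (√DE 1.2 to 3.9), and the association error rate from 5.3% to 50%.

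**5. Simulation check** (beta-binomial, 60 patients, 4,000 runs per setting). At m = 20 and ICC 0.2, coverage of the naive interval was about 62%. The association test rejected in 13.4% of runs when both readings clustered and in 5.4% when only one did. At m = 20 and ICC 0.3 for both, it rejected in 22.1%.

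**6. Pairing.** The last simulation compared imaging and pathology positivity on the same nodes by an unpaired chi-square. Both had 10% positivity and imaging sensitivity was 0.8, so the hypothesis of equal rates was true. Over m = 10 to 30 and ICC 0 to 0.3 the test rejected in at most 0.5% of runs, against a nominal 5%. Here the P values are too large, because the test ignores the positive correlation between paired readings.

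**The case against.** The strongest reply is that the plan never says nodes are pooled. Several cues point to one row per patient: the regression uses patient covariates such as age, BMI and surgical time, with the node count among them; "Data are presented as mean" ± standard deviation; and the sample size counts patients. A per-patient percentage summarised by mean and SD, or a chi test on patients, would not treat correlated nodes as independent.

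That stands in part. A reader might infer that the plan as written pools nodes and so understates uncertainty. The text does not support that as fact, because the unit is simply not given. But the objective is worded as a percentage of nodes, and the cues are not a specification. A patient-level chi test would still ignore pairing.

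A reader might also infer that the plan's error bars are too narrow. It plans no interval and no test for the node percentage, so there are none yet. The width factor applies only if an interval is computed from pooled nodes.

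Finally, a reader might apply the percentage's design effect to the chi test and conclude that a nominal 5% test really runs at 25% to 45% (m = 20) or 16% to 31% (m = 10). Those rates belong to a test of a single pooled proportion, which is not planned. For the association test the corresponding rates are 7% to 23% and 6% to 15%.

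**Conclusion.** The concern holds as an omission with conditional consequences. The plan does not state the unit of analysis or how clustering and pairing are handled, for both parts of its primary objective.

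If nodes are pooled:

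- A naive interval for the node percentage is too narrow by a factor of about 1.4 to 2.6.
- A node-level association chi-square has a true error rate of about 6% to 23% if imaging and pathology results both cluster, and about 5% if only one does.
- An unpaired comparison of positivity rates can err the other way, rejecting far less often than 5%.

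It would therefore be wrong to say in general that the P values will be too small; they are unreliable in a direction that depends on the variant of the test. The first two sizes rest on an assumed 10 to 20 nodes per patient and ICC of 0.1 to 0.3; the third rests also on the assumed positivity and sensitivity. If the patient is the unit, the clustering problem disappears but the pairing problem remains.

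**What to change.** State the unit of each analysis, list the three examinations, and revise the Statistic analysis section as follows:

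1. Keep the node percentage, since it is the stated objective, and report it with a 95% interval that treats the patient as the cluster (bootstrap resampling of patients, or GEE with robust variance).
2. Add the percentage of patients with any positive node, with an exact 95% interval. This supplements the node percentage and does not replace it.
3. Replace the plain chi test with the coincidence rate (percent agreement) and kappa, each with a 95% interval. Compare positivity rates with a paired test at patient level: McNemar for two examinations, Cochran's Q for three. If agreement is analysed by node, use cluster-adjusted versions of all of these.

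The cost is wider intervals and a little more programming. No new data are needed, but node results must be kept linked to the patient and, for node-level agreement, to the same node across examinations.

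### The metastasis-risk regression forces in three variables that arise during or after surgery, and reads fourteen coefficients at P < 0.05 with no exploratory label

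*Combined protocol and SAP*

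**What the plan says.** The Statistic analysis section describes one model: "Multiple linear regression analysis was applied to evaluate the risk of lymphatic metastasis related to fourteen independent variables". The qualitative predictors are hypertension, diabetes, "diagnosis according to the FIGO staging system and the pathological tumor type". The others are introduced as "eight quantitative variables (age, BMI, the number of lymph nodes", followed by the time from biopsy to operation and then "surgical time, surgical bleeding, postoperative anticoagulant time, preoperative value of Hb, preoperative value of RBC and preoperative value of Hct". On entry the plan says "All independent variables were incorporated into the model using the method of" Enter, so nothing is selected out. For all analyses, "the level of statistical significance was set at" P < 0.05. There is no multiplicity rule, and the regression is not called exploratory.

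The sentence before the model reads "The specific number and percentage of pelvic and abdominal lymph nodes that are invaded by tumor cells are collected". It is not tied to the regression, and the plan does not choose between number and percentage as the dependent variable.

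The Sample size section says "We propose to enroll 70 participants including 35 patients in the control group and the others in the experimental group", with an effective size of 60 after dropout. The Trial design section randomises patients with respect to lymphadenectomy. It does not say whether control patients also supply nodal pathology. Risk factors for metastasis appear in neither the Study objectives nor the Trial design section.

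**The concern.** A risk factor has to precede what it predicts. Metastasis found in nodes taken at the primary operation was there before the operation began. Operating time, blood loss and anticoagulation afterwards cannot have contributed to it. They can follow from it, because more extensive disease may mean a longer and bloodier operation. They can also track how thorough the dissection was, and so how many positive nodes were found.

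Forcing them in has two possible effects. One or more may be reported as a risk factor for metastasis. And adjusting for a consequence of the outcome removes part of the association that belongs to a genuine preoperative predictor, so that predictor may look weaker than it is.

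Separately, fourteen P values are each read at the same threshold, so a chance finding can be presented as an established risk factor.

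**Working it through.** **1. Count of predictors.** Four qualitative variables are named. The quantitative list runs: age, BMI, number of nodes, biopsy-to-operation interval, operating time, blood loss, anticoagulation time, Hb, RBC, Hct, which is ten. With the stated eight, 4 + 8 = 12. With the listed ten, 4 + 10 = 14, which reproduces the plan's fourteen. The word eight is the error.

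**2. Timing of each predictor, judged by its name.**

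| Group | Variables | Could precede metastasis? |
|---|---|---|
| Known before surgery | age, BMI, hypertension, diabetes, biopsy-to-operation interval, Hb, RBC, Hct, tumour type | Yes, or at least measurable before nodal status is known (tumour type assumed taken from biopsy) |
| Depends on a definition not given | FIGO stage, number of lymph nodes | Circular if the stage incorporates nodal status, or if the nodes are invaded nodes |
| During or after surgery | operating time, blood loss, anticoagulation time | No |

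**3. Patients available.** If everyone contributes, n is 60 to 70. If only one randomised group has nodal pathology, n is 60/2 = 30 to 70/2 = 35. With one parameter per variable, residual degrees of freedom are n − 15: 45, 55, 15 and 20 for n = 60, 70, 30 and 35. They are fewer if FIGO stage or tumour type needs several terms.

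**4. Chance findings.** For fourteen independent tests, 1 − 0.95^14 = 51%. In one regression the tests share a residual variance, so this was simulated: least squares, no true effects, independent normal predictors and 4,000 datasets per setting. Assumed inputs were 10–20% of patients node-positive, about 20 nodes examined each, and an outcome of node percentage, node count or yes/no.

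| n | At least one P < 0.05 among fourteen |
|---|---|
| 60 | 44.8–48.0% |
| 70 | 45.5–48.4% |
| 30 | 38.0–40.7% |
| 35 | 40.5–43.1% |

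Error per coefficient was 4.7–5.3%. Repeat runs gave 44–48% at 60–70 and 37–42% at 30–35. Correlating Hb, RBC and Hct at 0.9 barely changed the result. With the three surgical variables removed, eleven predictors remain and the figure at 60–70 is still 38–41%.

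**5. What the model can still detect.** Each coefficient is adjusted for thirteen others, so power at two-sided 0.05 is approximately Φ(atanh(r)·√(n − 16) − 1.96), where r is the partial correlation.
- r = 0.30, n = 60: 0.3095 × √44 = 2.05, and Φ(0.09) is about 54%.
- r = 0.40, n = 60: 0.4236 × √44 = 2.81, and Φ(0.85) is about 80%.

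Simulated values agree:

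| n | r = 0.30 | r = 0.40 |
|---|---|---|
| 60 | 54.5% | 81.0% |
| 70 | 63.1% | 88.1% |
| 30 | 21.8% | 36.8% |
| 35 | 27.7% | 47.0% |

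**6. Size of the timing fault (illustration only).** This needs inputs the documents do not give. Assume 60–70 patients, 10–20% node-positive, one true preoperative predictor (log-odds 1.0 per SD), a percentage or count outcome, and each of the three surgical variables higher in node-positive patients by the stated shift.

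| Shift | Any of the three flagged | Shrinkage of the true predictor |
|---|---|---|
| None | 14–15% | – |
| 0.25 SD | 18–26% | 2–3% |
| 0.5 SD | 31–53% | 6–10% |
| 1.0 SD | 64–93% | 21–31% |

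The flagging ranges are wide because they also depend on how many nodes are positive in a node-positive patient.

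**The case against.** The strongest reply is that this is a side analysis outside the stated objectives, and that related to can be read as association only. Its limited reach is granted. The association reading does not rescue the model, because the declared target is still risk of metastasis and the preoperative coefficients are still adjusted for things that happened later.

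It can also be said that the timing bias has no firm size. That stands. At a 0.25 SD shift it is small, and nothing in the documents supports a particular shift. The argument for removal rests on time order, not on the illustration.

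Several stronger readings are tempting and should not be drawn:
- *The model cannot identify risk factors.* Error per coefficient is near 5%, and power is 81–88% for a partial correlation of 0.40 at 60–70 patients.
- *A chance risk factor is more likely than not.* Every simulated figure is below 50%; only the independent-test formula reaches 51%.
- *The outcome is wholly undefined.* The preceding sentence and the primary objective point to the number or percentage of invaded nodes. What is missing is the link and the choice between them.
- *FIGO stage and node number are certainly circular.* That depends on definitions the plan does not give. Nodes examined could be a legitimate adjustment.
- *Linear regression, or keeping all of Hb, RBC and Hct, is shown to be wrong.* The simulations found near-nominal error for all three outcome types, and high correlation among the blood measures hardly altered the chance-finding rate.

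**Conclusion.** The point holds in a limited form. Including the three intraoperative and postoperative variables is wrong as written, and Enter guarantees that they stay. Its effect on the estimates cannot be quantified from the documents. Reading fourteen coefficients at P < 0.05 without an exploratory label gives about 44–48% odds of at least one false risk factor at 60–70 patients, and about 38–43% at 30–35, if there are no true effects. These figures assume independent predictors, one parameter per variable and 10–20% node-positive patients. This is multiplicity, not faulty standard errors. The eight-versus-ten discrepancy is a plain internal error.

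A reader might infer that the trial's main results are compromised. They are not: the node counts, the coincidence rate and the randomised comparison do not use this regression. The unnamed outcome and analysis set are missing detail to be supplied, not separate faults of the same weight. The point should be fixed, with high confidence.

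**What to change.** In the Statistic analysis section:
- Remove operating time, blood loss and postoperative anticoagulation time from the model and report them descriptively.
- Do not use invaded nodes, or any FIGO stage that incorporates nodal status, as a predictor of nodal metastasis.
- Label the regression exploratory and report estimates with 95% confidence intervals. Removing the three variables does not make this unnecessary, since eleven predictors still give 38–41% at 60–70 patients.
- Correct eight to ten in describing the present list, and restate the totals once the three variables are out.
- While editing, state whether the outcome is the number or the percentage of invaded nodes, and that the patients analysed are those with nodal pathology, naming the group or groups they come from.

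The cost is wording only: fewer adjusted coefficients and weaker claims about risk factors. No new data are needed.
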